8.2. Study Enrollment

- 8.2.1.Subject Identification
- 8.2.1.1 When a subject is considered eligible for entry into this clinical study, the subject will be allocated a study-specific number (Subject ID number). This number will be a unique identifier to the subject and written on each page of the CRF, and all other documentation relating to that subject.
- 8.2.1.2 The Subject ID number will consist of the study site testing location number and a sequential enrollment number at that location. For example, the third subject enrolled at site 1 would have a Subject ID 01-003.
- 8.2.1.3 The Principal Investigator (PI) or designee at each site will maintain a master log that will correlate each Subject ID number to the subject's name. This log will remain at the study site and will be confidential.
- 8.2.2.Subject Information
- 8.2.2.1 The following information will be obtained and documented on the appropriate CRF for all subjects enrolled in the study:
 - Age (age of the subject and of the person performing the test)
 - Sex
 - Race
 - Ethnicity
 - Level of education (of the person performing the test)

- Occupation(of the person performing the test)
- Exposure to someone with COVID-19 and when the exposure took place.
- Presence or absence of one or more COVID-19 symptoms, specifically: fever over 100° F or chills; cough; shortness of breath; difficulty breathing; muscle or body aches; fatigue; sore throat; headache; congestion or runny nose; new loss of taste or smell. Subjects will be asked how many days prior to the test the symptoms appeared.
- COVID-19 Vaccine Status including which vaccine, number of doses and date of last dose.

8.3. Group Assignment

8.3.1. Subjects will be assigned to one of two groups: Self-Test or Pediatric Test.

- 8.3.1.1 The Self-Test group will include the subject only. 8.3.1.2 The Pediatric group will include an adult tester and a pediatric subject (age 2 13).
- 8.3.2. The healthcare practitioner will first collect the SOC sample. To mitigate any potential bias which may affect the subject's visual interpretation of the Bio-Self COVID-19 Antigen Home Test result, the healthcare practitioner will not provide the SOC test results to the subject until after the results of the Bio-Self COVID-19 Antigen Home Test are read by the subject.
- 8.3.3.Subjects will be taken to an area where they cannot observe other subjects that are participating in this study and that simulates a home use environment.
- 8.3.4. The subject (or adult tester) will be provided with the Bio-Self COVID-19 Antigen Home Test and the Quick Reference Instructions (QRI).
- 8.3.5. After a minimum of 15 minutes after the SOC sample collection, the subject will be asked to conduct the test using the QRI. This includes collection of the sample, conducting the test, reading and interpreting the test results.
- 8.3.6. After a minimum of 15 minutes after the subject (or adult tester) sample collection, the healthcare practitioner will collect the nasal sample from the subject, that will be used for the Comparator.
- 8.3.7. A minimum of 15 minutes is required between each sample collection. The subject will be asked to blow their nose prior to collecting each sample.
- 8.3.5.1 The comparator sample will be labeled with the subject's study identification number.
- 8.3.5.2 The comparator sample will be shipped to the CLIA laboratory conducting the RT-PCR test. A Ct value will be obtained for all RT-PCR positive samples. A minimum of 30 positive samples will be sequenced.
- 8.4. COVID-19 RT-PCR Inconclusive Result
 - 8.4.1.If the result from the COVID-19 RT-PCR Test is inconclusive, the laboratory should repeat the COVID-19 RT-PCR test. If the test result is inconclusive a second time, the results should be reported as inconclusive, and the subject should be re-tested.
 - 8.4.2.Contact the subject and request that they return for a retest. Confirm a time and date for an unscheduled visit.

8.4.3. Follow the steps under Section 8.3.2 - 8.3.5.

9. Problem Reporting

If problems occur during the conduct of the study, the clinical monitor should be notified within five (5) days of incident.

10. Premature Study Termination or Suspension

10.1. This study may be suspended or prematurely terminated by the sponsor or the investigator immediately upon notice for any cause. Written notification via email or post, documenting the reason for study suspension or termination, will be provided by the suspending or terminating party. If the study is prematurely terminated or

suspended, the Principal Investigator will promptly inform the IRB and will provide the reason(s) for suspension or termination.

- 10.2. Circumstances that may warrant termination include, but are not limited to:
 - Insufficient adherence to protocol requirements.
 - Data that are not sufficiently complete and/or evaluable.
 - Determination of futility

11. Safety Considerations

11.1. Safety Warnings and Precautions

Handle all samples as potentially infectious according to universal precautions and good laboratory practices (GLP). Use an appropriate disinfectant for decontamination. Store and dispose of these materials and their containers in accordance with local regulations and guidelines.

- 11.2. Definition of Adverse Events
 - 11.2.1. An Adverse Events (AE) is any untoward medical event that occurs to the subject during the course of a study (with onset after the first study-specific procedure), whether or not that event is considered study-related.
 - 11.2.2. An adverse event may be mild, moderate or severe and are usually unexpected.
 - 11.2.3. All adverse events observed by the Principal Investigator or reported by the subject, must be reported to the Sponsor within 24 hours. To report an adverse event, the Principal Investigator will complete an adverse event form or relevant form.
 - 11.2.4. Adverse events will be considered study-related if the event follows a reasonable temporal sequence from a study related procedure and could readily have been produced by that study procedure. For the purpose of this study, only the collection of nasal nares swabs is considered to be the study procedures.
- 11.3. Reporting of Serious Adverse Events
 - 11.3.1. A Serious Adverse Event (SAE) is any adverse event that:
 - led to death
 - led to a serious deterioration in the health of the subject that either resulted in a lifethreatening illness or injury, or a permanent impairment of a body structure or a body function, or in-patient hospitalization or prolongation of existing hospitalization, or in medical or surgical intervention to prevent life-threatening illness or injury or permanent impairment to a body structure or a body function
 - led to foetal distress, foetal death or a congenital abnormality or birth defect
 - 11.3.2. Hospitalization is defined as greater than 24 hours in the hospital.
 - 11.3.3. All serious adverse events must be reported to the Sponsor by telephone within 24 hours of the Principal Investigator becoming aware of it.
 - 11.3.4. The Sponsor will be contacted on the following numbers: Contact Name: [name]

[contact]

- 11.3.5. The Principal Investigator should institute appropriate therapeutic and follow-up measures in accordance with good medical practice but should notify the monitor of such actions and record them in the Subject's CRF. Each telephone reported reaction must be reported in writing to the monitor within 10 working days of the event.
- 11.3.6. It is also the responsibility of the Principal Investigator to inform the representative of the appropriate IRB in a timely manner.

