6.4.1. Mechanism of Action

Bio-Self COVID-19 Antigen Home Test is immunochromatographic and uses double-antibody sandwich method to detect nucleocapsid protein from SARS-CoV-2 virus. During detection, the treated samples are added to the sample well of the test cartridge. When the concentration of SARS-CoV-2 antigen in the specimen is higher than the minimum detection limit, the viral antigen will form complexes with labeled antibodies first. Under chromatography, the complexes move forward along the nitrocellulose membrane until captured by pre-coated monoclonal antibodies of SARS-CoV-2 in the detection zone on the nitrocellulose film (Test line – T) to form a pink/purple reaction line on the detection zone, indicating the result is positive. Conversely, if there is no viral antigen or the concentration of antigen in the specimen is below the minimum detection limit, no pink/purple reaction line appears in the detection zone and the result is considered negative. Regardless of whether or not the sample contains viral antigens, the pink/purple reaction line that appears in the quality control zone (Control line – C) is the criterion for determining if the chromatography process is performing properly.

6.4.2.Device Output

Bio-Self COVID-19 Antigen Home Test is designed to be visually read by detecting a visible color band.

- 1. A test line (T) and control line (C) indicate a positive result.
- 2. A single control line (C) indicates a negative result.
- 3. A test line (T) only, or the absence of the control line (C) and test line (T), or blurred lines indicate an invalid test.

Positve Result

C-Line	T-Line	Result
Pink/purple	Pink/purple	Positive

Negative Result

C-Line	T-Line	Result	
Pink/purple	Colorless	Negative	

Invalid Result

C-Line	T-Line	Result
Colorless	Colorless or pink/purple	Invalid, retest

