12.2. Responsibility of Investigator

The Principal Investigator is responsible for the proper conduct of the study at their site(s). The investigator will ensure that the study is conducted in compliance with GCP, the protocol, the Clinical Study Agreement, and applicable regulations in 45 CFR 46, and any other applicable regulatory requirements. These requirements include:

- Obtaining IRB approval for the study and related documents before study initiation and enrolling Subjects.
- Obtaining informed consent from each subject in accordance with 21 CFR Part 50, as applicable.
- Protecting the rights, safety, and welfare of Subjects under their care.
- Reporting adverse events.
- Coordinating and providing reasonable medical care to subjects for an adverse event related to study participation.
- Reporting protocol deviations to the sponsor and IRB per IRB requirements.
- Maintaining traceability and secured storage of all test kits and study samples.
- Ensuring confidentiality of all study documents, procedures, and study samples.

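### The relatedness rule in 11.2.4 counts only swab collection as a study procedure, so an adverse event caused by handling or running the kit cannot, read literally, be classed as study-related

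*Combined protocol and SAP*

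**What the plan says.** Section 11.2.1 defines an adverse event as "any untoward medical event that occurs to the subject during the course of a study", with onset after the first study-specific procedure, and "whether or not that event is considered study-related". Section 11.2.3 adds that "All adverse events observed by the Principal Investigator or reported by the subject, must be reported to the Sponsor within 24 hours".

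Section 11.2.4 sets the causality rule. It opens with "Adverse events will be considered study-related if the event follows a reasonable temporal sequence from a study related procedure", requires also that the procedure could readily have produced the event, and ends by saying that "only the collection of nasal nares swabs is considered to be the study procedures". Sections 6.3.1 and 11.4.1 carry the same premise: each names swab collection as the only study-related procedure that could affect subject safety.

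Section 8.3.5 describes what the lay user is asked to do: "This includes collection of the sample, conducting the test, reading and interpreting the test results". Section 6.4.1 shows that handling continues after the swab: "During detection, the treated samples are added to the sample well of the test cartridge". Section 11.1 asks for all samples to be handled as potentially infectious.

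Section 8.3.1.2 describes the Pediatric group as an adult tester together with a pediatric subject aged 2 to 13.

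**The concern.** The study puts a home-use kit into lay hands, some of them working with a young child present. Swab discomfort is one source of harm; handling the treated sample and the cartridge is another. Under 11.2.4 only the first can count as study-related. If a lay user were hurt while running the kit, an investigator following the rule would have to record an event that the study caused as not study-related. A report of no related events from kit use would then reflect the definition and not what was observed.

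A second, smaller question concerns the adult tester. In the Pediatric group that person runs the kit, while the adverse event definition speaks of the subject. The reader cannot tell whether harm to the tester is to be recorded as an adverse event.

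**Working it through.** The protocol gives no figure to reproduce here and the point rests on no rate or sample size, so the check sets the sections side by side.

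**Relatedness**

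1. Under 11.2.4 the label requires a study procedure that precedes the event and could readily have produced it.
2. The same paragraph limits study procedures, for this study, to nasal swab collection.
3. Section 8.3.5 sits in Section 8, Study Procedures. It lists sample collection and conducting the test as separate items, so running the kit cannot be read into collection.
4. Section 6.4.1 confirms a step after collection, in which the sample has been treated and is placed in the cartridge.
5. Section 11.1 accepts that sample handling carries a hazard.
6. An event caused at the steps in 3 and 4 therefore has no qualifying procedure under 2, and fails the test in 1. Sections 8.3.5 and 11.2.4 use the idea of a study procedure in two different senses.

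**What depends on the label**

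| Provision | Depends on relatedness? |
|---|---|
| Being an adverse event (11.2.1) | No |
| Report to sponsor within 24 hours (11.2.3) | No |
| Serious event: telephone report, therapeutic measures and follow-up, IRB notice (11.3.3, 11.3.5, 11.3.6) | No |
| Investigator's duty to coordinate care (12.2) | Yes, but on a wider phrase than that in 11.2.4 |
| Statistical analysis (Section 13) | No safety analysis by relatedness is planned |

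The wording in 12.2 is "Coordinating and providing reasonable medical care to subjects for an adverse event related to study participation". It does not refer to 11.2.4, and running the kit is part of participating in the study.

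**Adult tester**

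- Pointing to the tester not being the subject: 8.3.1.2 names the two separately; 8.3.4 and 8.3.6 write the subject or, alternatively, the adult tester; 8.2.2.1 records the age of the subject and of the person performing the test as two items.
- Pointing the other way: the design text in Section 5 and Section 6.8 has the lay person testing either themselves or a further study participant, which implies that the tester participates too. Section 8.3.5 asks the subject to conduct the test and makes no pediatric exception. The exclusion in 7.3 for prior medical or laboratory training makes little sense for a young child unless it reaches the tester.

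No section settles the matter. For scale, 13.1 requires at least 30 subjects under 14 and allows up to 600 subjects. That is 30 / 600 = 5% of subjects at the maximum, and a larger share if enrollment stops earlier with the same 30 children.

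**The case against.** The strongest reply is that nothing is lost. Every untoward event in a subject is an adverse event and reaches the sponsor within 24 hours, serious events are handled without regard to cause, and no table by relatedness is planned. This stands, and it limits the point to a label.

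It can also be said that 6.3.1, 11.2.4 and 11.4.1 agree with one another, which suggests a deliberate judgement that only the swab carries risk. That explains the wording, but a judgement about where risk lies does not justify excluding the other steps from causality assessment in advance. The protocol gives no reagent composition or toxicity and describes no kit-handling injury, and the Quick Reference Instructions are not reproduced. Specific harms such as a splash are therefore illustrations only, and the documents do not show that kit handling is the main risk of the device.

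The rule is phrased as a condition for being related and does not say outright that everything else is unrelated. The closed list of procedures makes that the natural reading, but it remains an inference.

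A reader might infer two stronger conclusions. One is that harm to the adult tester is never an adverse event. The documents do not support this: the tester's status is undefined and the text points both ways. There are also other routes. Section 9 sends problems to the monitor within five days, and the investigator agreement requires prompt IRB reporting of unanticipated problems involving risk to subjects and to others. These routes assign no adverse event causality, and Section 9 is slower than 24 hours, but the event would not go unseen. The other is that 11.2.4 narrows the investigator's duty of care. It does not, because 12.2 uses its own, wider phrase.

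**Conclusion.** The point holds as a minor inconsistency. Read literally, 11.2.4 prevents any event caused by handling or running the kit from being classed as study-related, although 8.3.5 makes those steps part of the study procedures. The consequence is causality misclassification in subjects, with no loss of events and no effect on PPA, NPA or sample size. Separately, it is unclear whether the adult testers of at least 30 children come under the adverse event definition; this is an ambiguity to resolve and not an established exclusion.

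The conclusion assumes that investigators apply 11.2.4 as written. The documents give no frequency for kit-handling events; it is probably low, so the practical effect may be small.

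**What to change.** - In 11.2.4, define study procedures for relatedness as swab collection plus the kit handling and test steps in 8.3.5.
- Reconcile with this the sentences in 6.3.1 and 11.4.1 that name swab collection as the only study-related procedure affecting safety.
- In 11.2.1, state that events in the adult tester are captured. The serious event definition in 11.3.1 builds on the adverse event definition and would follow.

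The cost is an amendment to protocol and adverse event form wording, with matching consent text. The downside is that a few more events may be classed as related. No change to design, enrollment or analysis is needed.

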11.4. Possible Risks Associated with Study Procedures

- 11.4.1. The only study-related procedures that could impact subject safety is in the collection of a direct anterior nares (nasal) swab. The risks of collecting a nasal nares swab may include symptoms associated with standard collection practices such as slight pain, minor bleeding. Subjects will be identified using a study specific number at the time of enrollment. All study forms and any associated laboratory reports will be labeled with the subject number. No identifiable patient information will be provided to the Sponsor. No patient treatment or management decisions will be based on any results generated from this study, with the exception of the Standard of Care sample.
- 11.4.2. Information collected for this study is confidential. However, officials of FDA or other regulatory agencies may research records during ordinary course of carrying out their functions. A sponsor representative may also inspect research records to make certain the study data is accurate. The Investigator, institution, regulatory agencies and Sponsor will protect the confidentiality of the records.
- 11.4.3. No medical decisions will be based on investigational assay results generated as part of the study.

12. Regulatory and Administrative Requirements

12.1. FDA Guidance on EUA

FDA Guidance on EUA testing and data acknowledges these products are not subject to 21 CFR 812 noting all other human Subject protection regulations (45 CFR 46) apply. This study does not meet the definition of a clinical investigation as defined by 21 CFR 812 and is not subject to IRB surrogate determination of risk. This study is, however, a non-significant risk (NSR) study in that nasal sample collection is not considered invasive and the test results will not be used to manage clinical care. Implementation of this study will include waiver of otherwise-applicable GCPs to accommodate the emergency response COVID-19 diagnostic testing needs during the declaration time period.

12.2. Responsibility of Investigator

The Principal Investigator is responsible for the proper conduct of the study at their site(s). The investigator will ensure that the study is conducted in compliance with GCP, the protocol, the Clinical Study Agreement, and applicable regulations in 45 CFR 46, and any other applicable regulatory requirements. These requirements include:

- Obtaining IRB approval for the study and related documents before study initiation and enrolling Subjects.
- Obtaining informed consent from each subject in accordance with 21 CFR Part 50, as applicable.
- Protecting the rights, safety, and welfare of Subjects under their care.
- Reporting adverse events.
- Coordinating and providing reasonable medical care to subjects for an adverse event related to study participation.
- Reporting protocol deviations to the sponsor and IRB per IRB requirements.
- Maintaining traceability and secured storage of all test kits and study samples.
- Ensuring confidentiality of all study documents, procedures, and study samples.

12.3. Responsibility of Sponsor

12.3.1. The sponsor has the overall responsibility for the conduct of the study, including assurance that the study meets the FDA EUA regulations and other regulatory requirements as applicable.

The sponsor's study-related duties and functions may be transferred to a contract research organization (CRO).

12.4. Protocol Deviations

12.4.1. A protocol deviation is failure to comply with the requirements specified within the clinical study protocol or IRB requirements. Investigators are not allowed to deviate from the protocol

except when a deviation is necessary to protect Subject's rights and well-being, or the scientific integrity of the study.

- 12.5. Changes to Protocol
 - 12.5.1. In the event the study protocol is amended, the monitor will provide the Principal Investigator with the protocol amendment(s) and a revised protocol.
 - 12.5.2. Protocol amendments that affect the Subject rights, safety, or welfare must be submitted to and approved by the IRB. The Investigator must be notified of the approval, in writing, prior to implementation.
- 12.6. Reconciliation of Study Material, Supplies and Samples

The Sponsor will supply sufficient quantities of study materials and supplies to enable the site to complete the study and the site will return all unused materials and supplies to the Sponsor or dispose of according to provided instructions. The site is required to maintain the inventory of these materials provided and document the reconciliation of these materials. If materials are disposed at the study site, the Investigator must provide the Sponsor with a signed record of disposition.

13. Statistical Considerations

Except where otherwise specified, the following general principles apply to the planned statistical analyses. All statistical analysis will be conducted using a current version 9.4 (or later) of SAS (SAS Institute Inc., Cary, NC), Excel version 2010 or later, or other widely accepted statistical or graphical software as required. Continuous variables (e.g., age) will be summarized by the number of subjects; mean, standard deviation and median. Categorical variables (e.g., sex) will be summarized with frequency counts and percentages. Confidence intervals (CI) may be presented, where appropriate, using the exact method for categorical variables. In general, percentages will be displayed to 1 decimal place.

